With 40 patients treated at 10 mg/kg Q2W, the study has >90% power to rule out a >30% RR if <8 patients respond (i.e., probability of observing < 8 responses is <10% when true RR is 30%).

Part F NSCLC 2L+ PD-L1 positive (single arm)

With 40 patients treated at 2 mg/kg Q3W, the study has ~90% power to test the null hypothesis of RR =10% at 2.5% type I error rate (one-sided) when the true RR is 30%. A p-value of 2.5% approximately corresponds to an empirical RR of 22.5% (9/40).

Part F NSCLC 2L+ PD-L1 positive (randomized)

Approximately 250 patients will be randomized (3:2) to 10 mg/kg Q3W and 10 mg/kg Q2W. The randomization may be stratified by PD-L1 expression level based on a preliminary cutoff point once available (see Section 3.5.5.4 for details). With 250 patients, the study has approximately 95% power to detect a 15% difference in RR between the two doses at type I error rate of 10% (one-sided) assuming that the RR at 10 mg/kg Q3W is 10%.

Enrollment of patients with weakly positive tumors will be capped at 50% so that at least 75 patients with strongly positive tumors will be treated at 10 mg/kg Q3W. With 75 patients treated at 10 mg/kg Q3W, the study has 85% power to detect a 15% difference in RR between pembrolizumab (MK-3475) and historical control which is conservatively estimated to be 15% (i.e., 30% vs 15%) at type I error rate of 2.5% (one-sided). A p-value of 2.5% approximately corresponds to an empirical RR of 25% (i.e., the lower bound of the 95% CI for an empirical RR at 25% will exclude 15%). With 50 patients at 10 mg/kg Q2W, the study has 68% (or 89%) power to detect a 15% (or 20%) difference in RR between pembrolizumab (MK-3475) and historical control at type I error rate of 2.5% (one-sided). A p-value of 2.5% approximately corresponds to an empirical RR of 28% (i.e., the lower bound of the 95% CI for an empirical RR at 28% will exclude 15%). If 10 mg/kg Q2W has comparable anti-tumor effect to 10 mg/kg Q3W in the population, the two doses will be pooled for a joint analysis as appropriate. Regardless, if the primary analysis in the biomarker strongly positive population is positive a step-down analysis will be performed to assess all biomarker positive patients including patients with weakly positive tumors.

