As a comparison to interim analyses, [Table 3-7](#) presents outcome of interest in the ipilimumab-naïve population at the final analysis based on various hypothetical sample sizes. For N varying from 30 to 45, an observed RR of approximately 20-23% OR a DCR of approximately 44-47% is generally required to cross the efficacy bar for a positive study (the bars will be lower when sample size is greater – data not shown in table). If the study objective is not met in the all-comer ipilimumab-naïve population, an exploratory analysis will be conducted in a "biomarker positive" subpopulation determined by the PD-L1 cut-off level. Such an analysis will be only performed if the primary biomarker hypothesis is confirmed, i.e., there will be statistical concordance between PD-L1 expression levels at baseline and maximum total tumor volume reduction (%) produced by pembrolizumab (MK-3475). A Hochberg procedure with type I error rate of 5% (one-sided) will be applied to assist with the analysis.

Table 3-7

Efficacy Outcome of Interest in Ipilimumab-Naïve Population at the Final Analysis

	Study RR (null=10%)		Study DCR (null=30%)	
	Patients with response (%)	Nominal p-Value	Patients with disease control (%)	Nominal p-Value
30	7 (23%)	2.6%	14 (47%)	4.0%
35	8 (23%)	2.0%	16 (46%)	3.6%
40	8 (20%)	4.2%	18 (45%)	3.2%
45	9 (20%)	3.2%	20 (44%)	2.8%

Part F 1L NSCLC PD-L1 positive Patients

For each dose level in Part F 1L, an interim analysis will be conducted after the first 20 patients have had a 3-month follow-up. The accrual to a dose level may be put on hold if ≤ 2 patients have a response. The probability of observing ≤ 2 responses out of 20 patients is $< 10\%$ when the true RR is 25%. After a review of totality of data including tumor volumetric change, disease control rate and safety, the Sponsor will make a decision on whether to resume the accrual.

Part F 2L+ NSCLC PD-L1 positive Patients

There is one planned interim analysis. The primary objective of the interim analysis is to potentially exclude patients with weakly positive tumors (based on final cutoff point) from further enrollment. Based on current projection, the randomized portion may take 11 months to accrue. More interim analyses may be conducted if the accrual rate is slower than expected.

The interim analysis will be conducted after 60 patients in the randomized portion have a minimum follow-up of 12 weeks, which is expected to occur approximately 7 months

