after the randomization. The final PD-L1 assay cutoff point for efficacy analyses will be determined before this IA will occur. The target response rate is 20% for interim futility decisions. As guidance, if less than 3 out of 30 patients with weakly positive tumors (i.e., <10%) have a confirmed response no further patients with weakly positive tumors (based on final cutoff point) will be enrolled. The probability of observing less than 3 responses is <4% when the true response rate is 20%. When sample sizes are slightly different, an empirical response rate of <10% will be used as a reference or futility decisions which will also take into account the totality of data. Because the two dose schedules may have different cutoff points, a subgroup analysis by dose schedule will be conducted to determine whether to exclude patients with weakly positive tumors for one schedule or for both (see Section 3.5.5.4 for more details).

Additional Interim Analyses

In addition to the above interim analyses, an interim analysis of Part C may be conducted after all patients have had a 3-month follow-up, interim analyses of Part B ipilimumab-refractory patients and Part D ipilimumab-naive patients (timings to be determined) may be conducted to assist with the dose-selection decision for planning phase 2 studies in melanoma patients, and interim analyses may also be conducted to determine the cutoff points for high PD-L1 patients in melanoma and NSCLC patients (see Section 3.5.5.4).

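### The stated <4% chance of crossing the Part F 2L+ futility bar at a true response rate of 20% is wrong: the exact value is 4.4% at n=30, and higher at nearby sample sizes under the SAP's own reference

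*Combined protocol and SAP*

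**What the plan says.** Section 3.5.9 plans one interim analysis in the randomized Part F 2L+ PD-L1 positive cohort, mainly to decide whether patients with weakly positive tumors should still be enrolled. On timing: "The interim analysis will be conducted after 60 patients in the randomized portion have a minimum follow-up of 12 weeks". On the benchmark: "The target response rate is 20% for interim futility decisions". The bar is worded as "As guidance, if less than 3 out of 30 patients with weakly positive tumors (i.e., <10%) have a confirmed response", in which case no more such patients are enrolled. The operating characteristic given for that bar is "The probability of observing less than 3 responses is <4% when the true response rate is 20" percent.

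Two further sentences bear on how far that figure reaches. One handles other sample sizes: "When sample sizes are slightly different, an empirical response rate of <10% will be used as a reference", with the totality of data also weighed. The other adds a second decision: "a subgroup analysis by dose schedule will be conducted to determine whether to exclude patients with weakly positive tumors for one schedule or for both". No probability accompanies either sentence, and the second has no bar.

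**The concern.** The probability tells the reader how unlikely it is that the guidance would close enrolment to weakly positive patients when the drug meets the 20% target. It is stated as a strict upper bound, and all its inputs are in the same paragraph, so it can be checked directly. It does not hold.

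The figure also applies to exactly 30 patients, a count the interim need not deliver. The trigger is 60 randomized patients. Section 3.5.5.4 allows stratification on a preliminary PD-L1 cutoff, whereas the interim classifies tumors by the final cutoff. The number of weakly positive patients may therefore differ from 30, and the 10% reference then applies. A reader who carries the <4% over to that case would understate the chance further. Section 3.5 says that no separate SAP will be issued, so this paragraph is the only reference for the operating characteristic.

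**Working it through.** **Inputs, all from Section 3.5.9:** n = 30; the bar is crossed with 0, 1 or 2 responses; true response rate 0.20; stated probability <4%. Responses are taken as independent with a common rate, and the 20% as the rate of responses countable at the interim.

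**1. The plan's own figure.** With X ~ Binomial(30, 0.20):

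P(X ≤ 2) = 0.8^30 × [1 + 30(0.25) + 435(0.25)²] = 0.001238 × (1 + 7.5 + 27.1875) = 0.001238 × 35.6875 = 0.0442.

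This is 4.4%, not below 4%.

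**2. Where <4% might come from.** A normal approximation has mean 6 and SD √(30 × 0.2 × 0.8) = 2.191.

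- Without continuity correction: Φ((2 − 6)/2.191) = 3.4%.
- With continuity correction: Φ((2.5 − 6)/2.191) = 5.5%.
- Exact, with a fixed bar of fewer than 3 and n = 31: 3.7%.

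The uncorrected approximation or a different n would give a value under 4%. The SAP does not say which method was used, so this is conjecture.

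**3. Neighbouring Part F statements, checked the same way.**

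- 1L interim ("an interim analysis will be conducted after the first 20 patients have had a 3-month follow-up"), at most 2 responses in 20 at a true rate of 25%: 0.75^20 × [1 + 20/3 + 190/9] = 0.003171 × 28.78 = 9.1%. The SAP says <10%, which is correct.
- 3L+ PD-L1 negative cohort (Section 3.5.7), fewer than 8 responses in 40 at a true rate of 30%: 5.5%. The SAP says <10%, which is correct.

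These two bounds hold under the exact binomial; the 2L+ one does not.

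**4. Nearby sample sizes under the 10% reference.** The largest count with an empirical rate below 10% is ceil(0.1n) − 1. The SAP does not define how different is slightly different; n = 26 to 35 is my choice of range.

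| n | Bar crossed at | Probability at true rate 20% |
|---|---|---|
| 26 | ≤2 | 8.4% |
| 27 | ≤2 | 7.2% |
| 28 | ≤2 | 6.1% |
| 29 | ≤2 | 5.2% |
| 30 | ≤2 | 4.4% |
| 31 | ≤3 | 10.7% |
| 32 | ≤3 | 9.3% |
| 33 | ≤3 | 8.1% |
| 34 | ≤3 | 7.0% |
| 35 | ≤3 | 6.1% |

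Worked examples:

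- n = 29: 0.8^29 × [1 + 7.25 + 25.375] = 0.0015474 × 33.625 = 0.0520.
- n = 31: 0.8^31 × [1 + 7.75 + 29.0625 + 70.2344] = 0.00099035 × 108.047 = 0.1070.

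The jump at n = 31 arises because 3/31 is 9.7%, so a third response no longer clears the bar. In this range n = 30 gives the lowest probability, and that is still above 4%.

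**The case against.** The strongest reply is that this hardly matters. The error at n = 30 is 0.4 points. The bar is labelled guidance and is weighed with the totality of data. Section 1.5 reports enrolment as complete, so no patient's entry depends on the correction. The 10.7% is the single worst value in a range I chose. All of this stands, and it is why the point is minor. It does not make the stated bound true.

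Two stronger readings are tempting, and the documents do not support either.

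**By schedule.** A reader might take the allocation ("Approximately 250 patients will be randomized (3:2) to 10 mg/kg Q3W and 10 mg/kg Q2W"), split 30 patients into 18 and 12, apply the 10% reference to each, and infer much larger chances of wrongly excluding one schedule. But the SAP offers that reference only for sample sizes slightly different from 30, which 18 and 12 are not. The stated reason for the by-schedule look is that the schedules may have different cutoffs, so the weakly positive patients need not divide 3:2. Section 3.5.5.4 also divides the Q2W patients into training and validation halves for a Q2W-specific cutoff. Any by-schedule probability would therefore describe a rule the SAP does not set.

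**Confirmation.** The bar counts confirmed responses at a minimum of 12 weeks. Section 2.4.1 (Part C rules, applied to Part F) puts the first scan at about Week 9 and confirmation at about Week 13, or optionally Week 18. A reader might infer that the real crossing chance is well above 4.4% because some responses would still be unconfirmed. That holds only if 20% means the eventual confirmed rate. The SAP calls it the target for interim futility decisions, which can equally be read as the rate countable at that date, and 4.4% then needs no adjustment. The documents give no distribution of follow-up or of response timing from which to size a lag.

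**Conclusion.** The stated bound is wrong as written; severity is minor. On the SAP's own inputs the probability is 4.4% at n = 30, about 0.4 points above the claimed limit. Under the SAP's 10% reference it is about 4% to 11% for n between 26 and 35. The n = 30 result needs only independent responses with a common rate and 20% taken as the rate of responses countable at the interim. The wider range also depends on my reading of slightly different.

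All these values are chances of crossing a non-binding bar, not of enrolment actually being closed. The stated figure belongs to the pooled analysis and gives no information about the by-schedule exclusion decision. The absence of a by-schedule bar limits what the figure covers; it does not support substituting another number.

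**What to change.** In Section 3.5.9, replace <4% with 4.4% (<5%) at n = 30. Add one sentence saying that, under the 10% reference, the probability at a true rate of 20% ranges from about 4% to 11% for nearby sample sizes (26 to 35). The sentence should make clear that these are chances of crossing a non-binding bar in the pooled analysis, with the response rate taken as the rate countable at the interim, and that they do not cover the by-schedule decision. No by-schedule or confirmation-lag probabilities should be added.

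The cost is one number and one sentence. No design, enrolment or analysis changes.

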3.6 LABELING, PACKAGING, STORAGE, DISPENSING, AND RETURN OF CLINICAL SUPPLIES

3.6.1 Patient and Replacements Information

Pembrolizumab (MK-3475) clinical supplies will be packaged to support enrollment of approximately 1047 patients.

All other medications will be provided by the investigator.

3.6.2 Product Descriptions

Investigational materials will be provided by the SPONSOR as summarized in [Table 3-8](#).

Table 3-8

Product Descriptions

Product Name & Potency	Dosage Form
Pembrolizumab (MK-3475) (SCH900475) 50 mg	Powder for injection

3.6.3 Primary Packaging and Labeling Information

Pembrolizumab (MK-3475) (SCH900475) supplies will be packaged in **glass vials** as described in [Table 3-9](#) below.

Table 3-9

Packaging of Clinical Supplies

Product Name & Potency	Fill Count	Dosing Instructions
Pembrolizumab (MK-3475) (SCH900475)	50 mg/vial	Administer as directed

Container label text may include the following:

• Packaging Lot ID #• Fill Count & Dosage Form	
• Dosing Instructions• Storage Conditions• Compound ID - Protocol #• Country regulatory requirements• SPONSOR address (If applicable)
---	---

3.6.4 Secondary Packaging and Labeling Information (kit)

Supplies may be packaged in **kit boxes containing 1 vial**. Kit configuration is subject to change as a result of packaging constraints.

If secondary packaging is utilized, label text may include the following:

• Packaging Lot ID #• Fill Count & Dosage Form	
• Dosing Instructions• Storage Conditions• Compound ID - Protocol #• Country regulatory requirements• SPONSOR address (If applicable)
---	---

3.6.5 Clinical Supplies Disclosure

This study is open-label; therefore, the patient, the investigator's site personnel and the SPONSOR are not blinded to treatment. Drug identity (name, strength) is included in the label text; disclosure envelopes are not provided.

3.6.6 Storage and Handling Requirements

Clinical supplies should be kept in a secured location as indicated on the label. The clinical supplies storage area at the site must be monitored by the site staff for temperature consistency with the acceptable storage temperature range specified in this protocol or in the product label attached to the protocol. Documentation of temperature monitoring should be maintained.

3.6.7 Standard Policies / Return of Clinical Supplies

Investigational clinical supplies must be received by a designated person at the study site, handled and stored safely and properly, and kept in a secured location to which only the investigator and designated personnel have access. Clinical supplies are to be dispensed only in accordance with the protocol. The investigator is responsible for keeping accurate records of the clinical supplies received from the SPONSOR, the amount dispensed to and returned by the subjects/patients, and the amount remaining at the conclusion of the study. In accordance with Good Pharmacy Practices, gloves should always be worn by study personnel if directly handling tablets or capsules that are returned (i.e., when counting returns). The Clinical Monitor should be contacted with any questions concerning investigational products where special or protective handling is indicated. All used vials should be properly disposed of immediately in biohazard bins. Unused or expired vials must be returned as indicated on the Contact Information page(s).

3.7 DATA MANAGEMENT

Information regarding Data Management procedures for this protocol will be provided by the SPONSOR.

3.8 BIOLOGICAL SPECIMENS

Information regarding biological specimens for this protocol will be provided by the SPONSOR.

4. ADMINISTRATIVE AND REGULATORY DETAILS

4.1 CONFIDENTIALITY

4.1.1 Confidentiality of Data

For Studies Conducted Under the U.S. IND

Particular attention is drawn to the regulations promulgated by the Food and Drug Administration under the Freedom of Information Act providing, in part, that information furnished to clinical investigators and Institutional Review Boards will be kept confidential by the Food and Drug Administration only if maintained in confidence by the clinical investigator and Institutional Review Board.

For All Studies

By signing this protocol, the investigator affirms to the SPONSOR that information furnished to the investigator by the SPONSOR will be maintained in confidence and such information will be divulged to the Institutional Review Board, Ethics Review Committee, or similar or expert committee; affiliated institution; and employees only under an appropriate understanding of confidentiality with such board or committee, affiliated institution and employees. Data generated by this study will be considered confidential by the investigator, except to the extent that it is included in a publication as provided in the Publications section of this protocol.

4.1.2 Confidentiality of Subject/Patient Records

For All Studies

By signing this protocol, the investigator agrees that the SPONSOR (or SPONSOR representative), Institutional Review Board/Independent Ethics Committee (IRB/IEC), or Regulatory Agency representatives may consult and/or copy study documents in order to verify worksheet/case report form data. By signing the consent form, the subject/patient agrees to this process. If study documents will be photocopied during the process of verifying worksheet/case report form information, the subject/patient will be identified by unique code only; full names/initials will be masked prior to transmission to the SPONSOR.

For Studies Conducted Under the U.S. IND

By signing this protocol, the investigator agrees to treat all patient data used and disclosed in connection with this study in accordance with all applicable privacy laws, rules and regulations, including all applicable provisions of the Health Insurance Portability and Accountability Act and its implementing regulations, as amended from time to time (“HIPAA”).

4.1.3 Confidentiality of Investigator Information

For All Studies

By signing this protocol, the investigator recognizes that certain personal identifying information with respect to the investigator, and all subinvestigators and study site

personnel, may be used and disclosed for study management purposes, as part of a regulatory submissions, and as required by law. This information may include:

- name, address, telephone number, and email address;
- hospital or clinic address and telephone number;
- curriculum vitae or other summary of qualifications and credentials; and
- other professional documentation.

Consistent with the purposes described above, this information may be transmitted to the SPONSOR, and subsidiaries, affiliates and agents of the SPONSOR, in your country and other countries, including countries that do not have laws protecting such information. Additionally, the investigator's name and business contact information may be included when reporting certain serious adverse events to regulatory agencies or to other investigators. By signing this protocol, the investigator expressly consents to these uses and disclosures.

For Multicenter Studies

In order to facilitate contact between investigators, the SPONSOR may share an investigator's name and contact information with other participating investigators upon request.

4.2 COMPLIANCE WITH LAW, AUDIT, AND DEBARMENT

By signing this protocol, the investigator agrees to conduct the study in an efficient and diligent manner and in conformance with this protocol; generally accepted standards of Good Clinical Practice; and all applicable federal, state, and local laws, rules and regulations relating to the conduct of the clinical study.

The Code of Conduct, a collection of goals and considerations that govern the ethical and scientific conduct of clinical investigations sponsored by Merck, is attached.

The investigator also agrees to allow monitoring, audits, Institutional Review Board/Independent Ethics Committee review, and regulatory agency inspection of trial-related documents and procedures and provide for direct access to all study-related source data and documents.

The investigator agrees not to seek reimbursement from subjects/patients, their insurance providers, or from government programs for procedures included as part of the study reimbursed to the investigator by the SPONSOR.

The investigator shall prepare and maintain complete and accurate study documentation in compliance with Good Clinical Practice standards and applicable federal, state, and local laws, rules and regulations; and, for each subject/patient participating in the study, provide all data, and upon completion or termination of the clinical study submit any

other reports to the SPONSOR as required by this protocol or as otherwise required pursuant to any agreement with the SPONSOR.

Study documentation will be promptly and fully disclosed to the SPONSOR by the investigator upon request and also shall be made available at the investigator's site upon request for inspection, copying, review, and audit at reasonable times by representatives of the SPONSOR or any regulatory agencies. The investigator agrees to promptly take any reasonable steps that are requested by the SPONSOR as a result of an audit to cure deficiencies in the study documentation and worksheets/case report forms.

International Conference of Harmonization Good Clinical Practice guidelines (Section 4.3.3) recommend that the investigator inform the subject's primary physician about the subject's participation in the trial if the subject has a primary physician and if the subject agrees to the primary physician being informed.

According to European legislation, a SPONSOR must designate a principal or coordinating investigator (CI) to review the report (summarizing the study results) and confirm that to the best of his/her knowledge the report accurately describes conduct and results of the study. The SPONSOR may consider one or more factors in the selection of the individual to serve as the CI (e.g., thorough understanding of clinical trial methods, appropriate enrollment of subject/patient cohort, timely achievement of study milestones, availability of the CI during the anticipated review process).

The investigator will promptly inform the SPONSOR of any regulatory agency inspection conducted for this study.

Persons debarred from conducting or working on clinical studies by any court or regulatory agency will not be allowed to conduct or work on this SPONSOR's studies. The investigator will immediately disclose in writing to the SPONSOR if any person who is involved in conducting the study is debarred, or if any proceeding for debarment is pending or, to the best of the investigator's knowledge, threatened.

In the event the SPONSOR prematurely terminates a particular trial site, the SPONSOR will promptly notify that site's IRB/IEC.

